## **11. APPENDICES**

## APPENDIX A. STUDY SCHEDULE OF EVENTS

Event	Screening	Baseline	Treatment					Follow-up
	Day -21 to Day -14	Day 1	Day 3	Day 4	Day 5	Day 6	Day 7	Day 14
	VISIT 1	VISIT 2	VISIT 3	VISIT 4	VISIT 5	VISIT 6	VISIT 7	VISIT 8
Signed and Dated Informed Consent	X							
Inclusion/Exclusion Criteria	X	X						
Medical History	X							
Concomitant Medications a	X	X	X	X	X	X	X	X
Complete Physical Exam	X							
Vital Signs (Body temperature, BP, HR, Resp. rate)	X b	X	X	X	X	X	X	X
CBC c	X							
Pregnancy Test, Serum or Urine	X	X						
Targeted Physical Exam d		X	X	X	X	X	X	X
Physical Examination of the Administration Site e		X	X	X	X	X	X	X
Nickel Sulfate and Vehicle Control Patch Placement and Interpretation	X	X						
Dose Administration		X	X	X	X	X	X	
Test Area Assessment			X	X	X	X	X	X
Trans-epidermal Water Loss Assessment f		X	X	X	X			

Event	Screening	Baseline	Treatment					Follow-up
	Day -21 to Day -14	Day 1	Day 3	Day 4	Day 5	Day 6	Day 7	Day 14
	VISIT 1	VISIT 2	VISIT 3	VISIT 4	VISIT 5	VISIT 6	VISIT 7	VISIT 8
Digital Photographs of the Allergen Test Sites f		X	X	X	X			
Chromometer Images of the Allergen Test Sites f		X	X	X	X			
AE/Toxicity Assessment		X	X	X	X	X	X	X

a Con meds within 21 days prior to dosing and through the follow-up assessment on Visit 8/Day 14 to be recorded.

b Include body temperature at screening visit.

c WBC (with differential), Hgb, Hct, and platelets.

d Includes positives on a review of systems and follow-up of findings from previous physical examinations.

e Conducted immediately before patch administration, after dose administration (Treatment Regimen 2), immediately after patch removal, and prior to and 10 minutes post-dose on Study Days 3-7, and Day 14.

f To be conducted at Baseline and on Days 3-5 and includes subject questionnaire (Days 3-5).

**APPENDIX B. INTERNATIONAL CONTACT DERMATITIS RESEARCH GROUP [ICDRG] SCORING SCALE****International Contact Dermatitis Research Group Scoring Scale**

Score	Interpretation
?	Doubtful reaction; faint macular erythema only
+	Weak (nonvesicular) positive reaction; erythema infiltration, possibly papules
++	Strong (vesicular) positive reaction; erythema, infiltration, papules, vesicles
+++	Extreme positive reaction; bullous reaction
-	Negative reaction
IR	Irritant reaction of different types

**APPENDIX C. NICKEL SULFATE ALLERGY SYSTEM****Application for Nickel Sulfate Concentration Determination:****Preparing Patch:**

Place a filter paper disc in the chamber and moisten thoroughly with the 1%, 2.5% or 5% nickel sulfate solution.

**Applying Patch:**

1. Skin should be clean, healthy, and free of ointments, lotions, powders, acne, dermatitis, scars, hair or any other condition that might interfere with the application of the chamber or interpretation of the results.
2. The subject should stand or sit in a relaxed position. Apply prepared patches to the back.
3. Affix tape to the skin at the lower end and slowly roll patches up the back, pushing out air. Gently press patch to skin to ensure an even distribution of allergens. Rub the tape gently but firmly to ensure good adherence.
4. Mark the four corners of each unit with Chemotechnique Skin Markers to indicate each unit's location on the subject's skin.
5. Subjects should refrain from exposing patch tests to excess moisture or sweat and should return for patch test removal in 48 hours.
6. Record in the source documentation the location of the patch and the nickel sulfate concentration for each location.

**Removing Patch:**

After 48 hours, remove the patch. The initial visual patch imprint on the patient's back indicates excellent occlusion.

**Reading the Results:**

1. Allow about 20 to 30 minutes for the transient skin irritation and visual patch imprints to subside before interpreting the test results.
2. Reading will be done at approximately 48 hours post application.
3. Use the Reading Plate to facilitate the reading.
4. Use the International Contact Dermatitis Research Group Scoring Scale to interpret the test results ([Appendix B](#)).

## APPENDIX D. PHOTOGRAPHIC PROCEDURE

### Serial Photography for Contact Dermatitis

**Locations:** ID card/color card view: 2 each Close-up view of target area(s): 2 each Anatomical location view of target area(s): 2 each

### **Digital Format Photography Equipment: Media: SD Memory card, 1GB**

Camera: Nikon D80 (10.2MP) Lens: Nikkor 60mm f2.8 Flash: Canfield TwinFlash system  
Other: Canfield MM scale arm attachment Blue deluxe felt backdrop (3'x8') Color card/Patient ID card holder

**Digital Format Photographic Considerations:** Each memory card will contain one patient photo session.

#### **Procedure:**

In these clinical photographs, for the duration of the study, the only variable allowed to change is the skin condition itself. Therefore, anything extraneous to the condition (jewelry, clothing, furniture, walls, etc.) is to be eliminated from the fields to be photographed, from the baseline through the final photographs. The necessity of good end-of-study photos should be stressed to the patients to ensure their cooperation. Lighting, framing, exposure and reproduction ratios must be held constant. In the end, the pictures should read like a time-lapse movie.

1. The supplied equipment is to be used exclusively for this study. Modifications, adjustments or repairs of the camera equipment are not to be undertaken without the expressed instruction of Canfield Scientific, Inc.
2. After obtaining informed consent, the patients are prepped for photography. All jewelry, makeup and clothing are to be removed from the photographic field prior to photography. Target area(s) are identified for photos. The supplied standardized blue deluxe felt background is to be used for the photographs. Do not use folded or crimped material.
3. Magnifications for digital camera: A standardized reproduction ratio (35MM film equivalent) of 1:3 (red index on lens focusing barrel) is used for the target area close-up views. Focusing at 1:3 is accomplished with the use of the mm scale arm attachment dictating distance. A standardized reproduction ratio of 1:9 (green index on lens focusing barrel) is used for the target area anatomical views. Focusing at 1:9 is accomplished by moving the camera/lens close to/away from the target area until it is in focus.
4. Apertures for digital camera: Each and every target area close-up view is taken at f/22. Each and every target area anatomical location view is taken at f/16.
5. SD is the media format used to capture images. If there is any doubt as to the correctness of technique or data, re-shoots are strongly urged.

6. Each SD memory card at every photographic session includes an exposure series of:
  - a. Two exposures of patient's ID card which includes the following legible information in black indelible ink: Protocol No. Date Investigator Number Visit Week Number Patient's Initials Patient's ID Number Photographer's Initials Color card
  - b. Two exposures of close-up view of target area(s)
  - c. Two exposures of anatomical location view of target area(s)
7. Upon completion of the photographic session, the contents of the SD memory card are uploaded to the Canfield Clinical Website once a patient's photographic session has been recorded on it. A secure, validated, compliant web server set up at Canfield is used for this secure transfer of study images by study sites. Images are transferred the day recorded. Remote access to all images by the sponsor is also provided. Only approved individuals by sponsor have access to the website.
8. Upon a successful upload of all images contained on the SD memory card, the memory card's images are deleted and the memory card re-used for the next photographic session. These memory cards are reserved for use on this project only. Any doubt as to the correctness of technique or data warrants a re-shoot then and there.
9. All images are monitored for technical adherence according to Canfield's internal SOPs. The study site is contacted if errors or deviation from photographic guidelines are observed. All communication to the study site relating to the photography is the responsibility of Canfield.
10. All supplied photographic equipment and photographic originals remain the property of the sponsor. One set of photography result report forms for all photographic time-points is supplied for the Investigators' study records.
11. Questions or problems regarding the photographic portion of this study protocol should be directed to the respective Canfield Project Manager assigned to the study.

**Canfield Scientific, Inc. [name] Telephone:** [REDACTED] **Toll-Free:** [REDACTED] **Facsimile:** [REDACTED] **E-mail:** [REDACTED]

## APPENDIX E. ABBREVIATIONS

ABBREVIATION	TERM
AE	Adverse event
BP	Blood pressure
BUN	Blood urea nitrogen
°C	Degrees Celsius
CAP	College of American Pathologists
CFR	Code of Federal Regulations
CLIA	Clinical Laboratory Improvement Amendments
CRF	Case report form
CTCAE	Common Terminology Criteria for Adverse Events
DESI	Drug Efficacy Study Implementation
EC	Ethics Committee
FDA	U.S. Food and Drug Administration
GCP	Good Clinical Practice
Hct	Hematocrit
Hgb	Hemoglobin
HIPAA	Health Insurance Portability Act of 1996
HIV	Human immunodeficiency virus
HR	Heart rate
IB	Investigator's Brochure
ICDRG	International Contact Dermatitis Research Group
ICF	Informed consent form
ICH	International Conference on Harmonization
ID	Intradermally
IND	Investigational New Drug
IRB	Institutional Review Board
NCI	National Cancer Institute
PHI	Personal Health Information
RH	Relative humidity
rHuPH20	Recombinant human hyaluronidase enzyme PH20
SAE	Serious adverse event

ABBREVIATION	TERM
SC	Subcutaneous
SD	Secure digital
SGOT	Serum glutamic-oxaloacetic transaminase
SGPT	Serum glutamate pyruvate transaminase
SOPs	Standard operating procedures
TEWL	Trans-epidermal water loss
USP	United States Pharmacopoeia
VAS	Visual analog scale
WBC	White blood cells

Pre-Treatment-emergent AE	AEs occur between the time the subject signs the informed consent document for the study to the time leading up to when that subject is first exposed to study drug.
Serious AE	An AE occurring at any dose that: results in death; is a life-threatening event; requires in-subject hospitalization or prolongation of an existing hospitalization; results in a persistent or significant disability/incapacity; results in a congenital anomaly/birth defect in the offspring of a subject who received study drug, or is any other important medical event.
Treatment-emergent AE	AEs with an onset time during or after the initial administration of study drug.
Treatment Regimens	Treatment Regimen 1 and Treatment Regimen 2

1. INTRODUCTION

This document outlines the statistical methods to be implemented during the analyses of data collected within the scope of Halozyme Therapeutics, Inc. Protocol HALO-114-201 [A prospective, randomized, double-blind, placebo-controlled, single-center study of the intradermal injection of rHuPH20 or placebo in subjects with nickel allergic contact dermatitis]. The purpose of this plan is to provide specific guidelines from which the analysis will proceed. Any deviations from these guidelines will be documented in the clinical study report (CSR).

2. OBJECTIVES

The primary objectives of the study are:

- Determine the treatment effect of rHuPH20 or placebo control injection on the exposure to topical nickel allergen (Treatment Regimens 1 and 2)
- Determine the time to onset and severity of cutaneous reaction to nickel allergen after pre-treatment with rHuPH20 or placebo control (Treatment Regimen 2)
- Assess the safety and tolerability of the rHuPH20 injection

Secondary objectives include:

- Proportion (%) of subjects who, with pre-treatment, have a ≥ 1 grade reduction of the cutaneous reaction to nickel sulfate in at least one patch region at 48 hours
- Proportion (%) of subjects with a ≥ 1 grade reduction of the cutaneous reaction to nickel sulfate in at least one patch region after treatment
- Proportion (%) of subjects that have a ≥ 1 grade reduction of the cutaneous reaction to nickel sulfate in at least one patch region at Days 4, 5, 6, 7 and 14.
- Safety and tolerability of the injection based on AEs, physical examinations, and vital signs

Descriptive-Only parameters include:

- Chromometer readings of the allergen test sites on Day 1, Day 3 (48 hrs), Day 4 (72 hrs) and Day 5 (96 hrs) after the placement of the patches
- TEWL (Trans-epidermal water loss) assessment on Day 1, Day 3 (48 hrs), Day 4 (72 hrs) and Day 5 (96 hrs) after the placement of the patches

3. STUDY OVERVIEW

This is a pilot Phase II, prospective, double-blind, placebo-controlled study to compare the efficacy, safety, and tolerability of rHuPH20 or placebo control administered

intradermally (ID) in the prevention and treatment of subjects with contact allergy to nickel. A maximum of 30 subjects may be enrolled to ensure that at least approximately 20 evaluable subjects complete the study. This study will be conducted at a dermatology unit.

There are two treatment regimens (Treatment Regimens 1 and 2) in this study, which will run in parallel. Within each regimen, four nickel sulfate patches will be used. The four patch areas will be randomized to rHuPH20 or placebo for each subject with 1:1 ratio. The randomization for Treatment Regimen 1 will be independent of the randomization for Treatment Regimen 2.

Figure 1: Study Treatment Arm Randomization

Treatment Regimen 1	rHuPH20 or Placebo (TR1-1)	rHuPH20 or Placebo (TR1-2)	rHuPH20 or Placebo (TR1-3)	rHuPH20 or Placebo (TR1-4)
Treatment Regimen 2	rHuPH20 or Placebo (TR2-5)	rHuPH20 or Placebo (TR2-6)	rHuPH20 or Placebo (TR2-7)	rHuPH20 or Placebo (TR2-8)

Subjects with a known history of contact allergy to nickel will be recruited. During the screening period, subjects will be tested to confirm the presence of cutaneous nickel sensitivity using 1, 2.5 and 5% nickel sulfate patches. The concentration of nickel sulfate for each subject that causes no greater than a ++ cutaneous reaction using the International Contact Dermatitis Research Group (ICDRG) scoring scale will be the concentration administered on Day 1. Once the concentration is determined for the subject, the patches in Treatment Regimen 1 and Treatment Regimen 2 will use the same concentration patches.

Treatment Regimen 1 (TR1-1 – TR1-4):

This regimen will assess the treatment of contact allergy to nickel: On Day 1, a single row of four patches (1, 2.5, or 5% nickel sulfate patches; determined for each subject during the Screening period) will be placed on the upper space on the upper back. After 48 hours, the patches will be removed and an assessment will be made of the reaction site as per the ICDRG scoring system. Each subject will receive in the center of the

cutaneous reaction an ID syringe push bolus injection of either rHuPH20 or placebo control. Each injection will be administered once daily for 5 days. Prior to each daily injection, subjects will be evaluated for efficacy, safety, and tolerability. A final evaluation will be conducted 7 days after the last dose of study treatment.

Treatment Regimen 2 (TR2-5 – TR2-8):

This regimen will assess the prevention and treatment of contact allergy to nickel sulfate. Each subject will receive in the center of each lower space on the back, either an ID syringe push bolus injection of rHuPH20 or placebo control. Exactly 10 minutes after the injection, a single row of four patches (1, 2.5, or 5% nickel sulfate patches; determined for each subject during the Screening period) will be placed over the center of the ID injection. After 48 hours, the patches will be removed and an assessment will be made of the reaction site as per the ICDRG scoring system. The subject will receive an ID injection of the same study drug from pre-treatment in the center of the cutaneous reaction once daily for 5 days. Subjects will be evaluated for efficacy, safety, and tolerability, on a daily basis. A final evaluation will be conducted 7 days after the last dose of study treatment.

For a given subject, the anticipated duration of time on study is up to 35 days, which include Visit 1 (screening, within 21 days prior to receiving study drug), Visit 2 (Day 1), Visit 3 (Day 3), Visits 4 – 7 (Day 4 – 7) and Visit 8 (Day 14).

4. GENERAL ANALYSIS CONSIDERATIONS

The statistical analyses will be reported using summary tables, figures, and data listings. Descriptive statistics will be used to summarize all efficacy variables. No formal statistical comparisons between treatments are planned. Continuous variables will be summarized with means, standard deviations, medians, minimums, and maximums. Categorical variables will be summarized by counts and by percentage of subjects in corresponding categories.

Individual subject data obtained from the case report forms (CRFs), local lab and any derived data will be presented by subject in data listings.

The analyses described in this plan are considered a priori, in that they have been defined prior to database lock and prior to breaking the blind. Any analyses performed subsequent to breaking the blind will be considered post-hoc. Post-hoc analyses will be identified in the CSR.

All analyses and tabulations will be performed using SAS® Version 9.1 on a PC platform. Tables and listings will be presented in RTF format. Figures will be presented in PDF format. Upon completion, all SAS® programs will be validated by an independent programmer. In addition, all program output will undergo a senior level statistical review. The validation process will be used to confirm that statistically valid methods have been implemented and that all data manipulations and calculations are accurate. Checks will be made to ensure accuracy, consistency with this plan, consistency within tables, and consistency between tables and corresponding data listings. Upon completion of validation and quality review procedures, all documentation will be collected and filed by the project statistician or designee.

5. ANALYSIS POPULATIONS

The ITT population will include all enrolled subjects (all subjects who got a subject identification number assigned at the time of study enrollment in anticipation of receiving a dose of study drug).

The Safety population will include all subjects who receive at least one dose of study drug.

The Evaluable population will include all evaluable subjects. An evaluable subject is one who has completed dosing (or prematurely discontinued the administration due to a toxicity) and has undergone sufficient assessments to allow an assessment of the tolerability of the administration.

A subject is considered to have undergone sufficient assessments to allow an assessment of the tolerability of the administration if the subject has at least one ICDRG score reported on Day 4 or later.

A subject is considered to have prematurely discontinued the administration due to toxicity if the subject has Adverse Event checked as the reason for not completing the study on the Study Completion/Termination CRF page, and has Drug Withdrawn as the action taken with study drug checked on the Adverse Event CRF page.

Efficacy analyses will be run on the Evaluable population and the ITT (Intent-to-Treat) population. Analyses run on the Evaluable population will be considered the primary analyses.

Safety analyses will be run on the Safety population.

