## **5.2. Subject Replacement/Completion Criteria**

Subjects who are not evaluable will be replaced. An evaluable subject is one who has completed dosing (or prematurely discontinued the administration due to a toxicity) and has undergone sufficient assessments to allow an assessment of the tolerability of the administration.

As this study is being conducted at a single site, the site personnel, in conjunction with the Sponsor, will make the determination when a subject will need to be replaced in the study. This information will be collected on the Enrollment Log. Each subject not meeting the completion criteria will be replaced by the enrollment of an additional subject. In the event that a subject withdraws from the study prematurely or does not meet the completion criteria, every effort will be made to document the reason for termination and obtain follow-up safety data.

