8. EFFICACY ANALYSES

Efficacy analyses will be carried out on both the Evaluable and the ITT analysis populations.

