8.1 Primary Variables

The primary efficacy endpoint will be based on the International Contact Dermatitis Research Group (ICDRG) Scoring Scale. Using the ICDRG Scoring Scale, each score will be assigned a Sponsor-defined “grade”. Scores with stronger reactions will be assigned grades with higher values with a maximum grade of 3; scores with weaker reactions will receive lower values with a minimum grade of 0. Grade assignments based on the ICDRG Scoring Scale are shown in the table below.

International Contact Dermatitis Research Group (ICDRG) Scoring Scale

Grade	Score	Interpretation
0	-	Negative reaction
1/2	?	Doubtful reaction; faint macular erythema only
1	+	Weak (nonvesicular) positive reaction; erythema, infiltration, papules, vesicles
2	++	Strong (vesicular) positive reaction; erythema, infiltration, papules, vesicles
3	+++	Extreme positive reaction; bullous reaction
NA	IR	Irritant reaction of different types

Treatment effect of rHuPH20 or placebo control injection on the exposure to topical nickel allergen will be assessed using ICDRG grades for Treatment Regimens 1 and 2 at Day 3 through Day 7 and Day 14.

Regimen 2 only: For each subject, the day of maximal ICDRG score will be determined for each injection type (rHuPH20 and Placebo). The maximal ICDRG score will be the highest score reported for each subject. If the maximal ICDRG score for a particular subject is reported more than one time, the first instance will be used to determine the day when the maximal ICDRG score was reached.

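### The primary set for the Regimen 2 48-hour grade is selected partly on events that happen after that grade is recorded

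*SAP*

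**What the plan says.** SAP Section 5 defines a single Evaluable population with two conditions, both required.

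- Dosing: "An evaluable subject is one who has completed dosing (or prematurely discontinued the administration due to a toxicity"). The toxicity route needs an adverse event as the reason for not completing the study, and the subject also "has Drug Withdrawn as the action taken with study drug checked on the Adverse Event CRF page".
- Assessments: they are sufficient "if the subject has at least one ICDRG score reported on Day 4 or later".

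On use, SAP Section 5 states: "Efficacy analyses will be run on the Evaluable population and the ITT (Intent-to-Treat) population". It then ranks the two: "Analyses run on the Evaluable population will be considered the primary analyses". SAP Section 8 repeats that both populations serve efficacy and makes no exception for any endpoint. Protocol Section 8 likewise names the evaluable subjects as the primary data set.

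The Day 3 grade is part of the primary variable in SAP 8.1, where the treatment effect is "assessed using ICDRG grades for Treatment Regimens 1 and 2 at Day 3 through Day 7 and Day 14". SAP 8.2 adds a Regimen 2 proportion at 48 hours (Day 3) as a secondary variable. Protocol 5.2 says of non-evaluable subjects: "Each subject not meeting the completion criteria will be replaced by the enrollment of an additional subject".

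**The concern.** Regimen 2 asks a prevention question as well as a treatment question, and prevention is the first hypothesis in Protocol Section 8 and SAP Section 9. The 48-hour answer is complete on Day 3: one set of injections on Day 1, patches for 48 hours, then the ICDRG grade. Nothing that happens later can alter it. The evaluability rule nevertheless uses later dosing and later scores to decide whose 48-hour grades enter the primary run. Its stated purpose is to make tolerability assessable, which is a different matter from whether the prevention outcome was observed.

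At stake are complete within-subject pairs in a small study, and a primary 48-hour result that describes only subjects who went on to meet the later conditions.

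**Working it through.** No figure in the plan can be reproduced here. The 20 evaluable subjects come with no power, effect size or dropout rate (Protocol 3.3, SAP 11). The check is to apply the definition, then to size the effect under stated assumptions.

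**1. Timing.** Scheduled injections per subject, from Protocol 3.1:
- Regimen 1: 4 sites × 5 days = 20.
- Regimen 2: 4 sites × (1 pre-treatment + 5 days) = 24.
- Total: 44. Only the 4 Regimen 2 pre-treatment injections precede the Day 3 grade; 44 − 4 = 40 follow it.

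**2. Applying SAP Section 5 to a subject who has her Regimen 2 Day 3 grades:**
- (a) Stops before completing dosing for a non-toxicity reason: out, with or without a Day 4 score.
- (b) Stops for toxicity with no score on Day 4 or later: out.
- (c) Stops for toxicity with a score on Day 4 or later: kept.
- (d) Completes dosing with a score on Day 4 or later: kept.

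Her 48-hour grades can be identical in all four cases.

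**3. How many might be lost.** Assumptions, not in the documents: each of the four visits on Days 4 to 7 is missed independently with probability p, and dosing is complete only if every visit is attended. Among subjects already scored and dosed on Day 3, the share dropped is 1 − (1 − p)^4:
- p = 2%: 1 − 0.98^4 = 7.8%.
- p = 5%: 1 − 0.95^4 = 18.5%.

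To reach 20 evaluable, the scored subjects needed are 20/0.922 = 21.7 or 20/0.815 = 24.5, so roughly 2 or 5 would be left out. With 20 evaluable, the enrolment cap of 30 limits the loss to 10 of 30 (33%).

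**4. What that could do to a 48-hour proportion.** Assume 8 of 20 evaluable subjects respond (40%; illustrative only). With k scored subjects left out, the proportion among all scored subjects lies between 8/(20 + k) and (8 + k)/(20 + k):
- k = 2: 8/22 to 10/22, or 36.4% to 45.5%.
- k = 5: 8/25 to 13/25, or 32.0% to 52.0%.
- k = 10: 8/30 to 18/30, or 26.7% to 60.0%.

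These are extreme bounds, with none or all of the omitted subjects responding. They are not expected shifts.

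**The case against.** The strongest reply is that little in the report depends on this rule.

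- The same efficacy analyses are run on ITT without imputation. ITT subjects with Day 3 grades at both site types are essentially the set one would want.
- The only efficacy table split by population is Table 6.1/6.2. It compares later days with Day 3, so requiring a later score is reasonable there.
- The Day 3 grades are shown by subject in Figure 1 and Listing 8 and judged by qualitative medical review (SAP 9.1). Neither display is restricted to Evaluable; Figure 1 needs only a record in the demographic and ICDRG datasets.
- No formal comparison is planned.

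All of this stands, and it limits the consequence. It does not remove the point. SAP 9.1 still asks for a proportion of subjects, which needs a denominator, and Section 5 gives precedence to the Evaluable one if the two runs differ.

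A reader might infer more than the documents support:
- **Arm imbalance.** Each subject carries two rHuPH20 and two placebo sites per regimen, so an exclusion removes both treatments.
- **A shift towards milder reactors.** This is conceivable, but the documents do not show it. Reactions above ++ at screening are excluded, and some subjects who stop for toxicity are kept under case (c).
- **Larger losses.** Counting all six dosing visits gives 1 − 0.98^6 = 11.4% or 1 − 0.95^6 = 26.5%. Days 1 and 3 do not belong in the count for someone already scored and dosed on Day 3. The 33% is a ceiling set by the enrolment cap, and the documents do not say how many non-evaluable subjects would have a Day 3 grade.
- **Any missed injection makes a subject non-evaluable.** The SAP does not define completion of dosing that strictly; step 3 assumes it.

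**Conclusion.** The point holds, and it is minor. In the run labelled primary, membership for a Day 3 outcome depends on events after Day 3. Subjects in cases (a) and (b) lose complete within-subject pairs from the primary 48-hour comparison, although they remain in the ITT run and the by-subject displays. Under the assumed miss rates and the strict reading of completed dosing, the loss is about 8% or 19% of subjects scored and dosed on Day 3, and it could be smaller under a looser reading. The direction of any resulting bias is unknown.

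A separate problem remains whichever set is used. SAP 8.4 makes Day 3 the baseline for grades in both regimens, so a reduction of at least one grade at 48 hours has no defined reference. A change of analysis set does not resolve that.

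**What to change.** In SAP Section 5, state that for the Regimen 2 Day 3 (48-hour) comparison the primary set is every subject who received the Day 1 Regimen 2 injections and has a Day 3 ICDRG grade at one or more rHuPH20 sites and one or more placebo sites, regardless of later dosing or visits. Keep the present Evaluable rule for Day 4 to Day 14 results, including Table 6.1, and for replacement.

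Protocol Section 8 names the evaluable subjects as the primary data set, so the same exception must be recorded there or the two documents will conflict. Make the change before the blind is broken; under SAP Section 4, analyses performed after that point count as post-hoc.

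The cost is a short addition to each document and a second efficacy denominator to explain. No new data or subjects are needed.
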